### 2.2 Secondary

2.21 Test the safety of single-agent MK-3475 in relapsed CLL/SLL (Arm A), other low grade B-NHL (Arm B), and CLL with Richter's transformation (Arm C).

2.22 Test the overall survival, progression free survival, treatment free survival, duration of response and time to next therapy of single-agent MK-3475 in relapsed CLL/SLL (Arm A), other low grade B-NHL (Arm B), and CLL with Richter's transformation (Arm C).

2.23 Test the complete response rate of single-agent MK-3475 in relapsed CLL/SLL (Arm A), other low grade B-NHL (Arm B), and CLL with Richter's transformation (Arm C).

2.24 Test the safety of MK-3475 in combination with the signal inhibitor (either Idelalisib or Ibrutinib) in relapsed CLL/SLL (Arm A) and CLL with Richter's transformation (Arm C).

2.25 Test the progression-free survival, treatment-free survival, duration of response and time to next therapy, as well as overall survival of MK-3475 in combination with the signal inhibitor (either Idelalisib or Ibrutinib) in relapsed CLL/SLL (Arm A) and CLL with Richter's transformation (Arm C).

2.26 Test the overall and complete response rates of MK-3475 in combination with the signal inhibitor (either Idelalisib or Ibrutinib in relapsed CLL/SLL (Arm A) and CLL with Richter's transformation (Arm C).

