### 7.3 For CLL patients with or without Richter's transformation (Arm A and Arm C), if a patient developed progressive disease (not tumor flare) at any time of the single-agent (MK-3475) therapy, or has stable disease without partial remission at the response

evaluation at month 3 of the single-agent (MK-3475) therapy, a commercially available FDA-approved CLL signal inhibitor can be added to MK-3475 (remain at the dose 200mg IV every 3 weeks). In this clinical scenario, if the patient had not used Ibrutinib in the past, Ibrutinib is recommended to be added using the standard FDA approved dose. However, the dose of Ibrutinib can be modified by treating physician based on concomitant medications or other clinical status. If the patient had progressed or had intolerable adverse events on Ibrutinib, Idelalisib is recommended to be added using the standard FDA approved dose. The dose of Ibrutinib or Idelalisib can be reduced/adjusted due to adverse events or concomitant medications according to the package inserts of the individual agent. If the patient had used both Ibrutinib and Idelalisib in the past, it is at the discretion of investigator/treating physician to decide which FDA-approved oral CLL therapy to use according to the package inserts of the individual agent and clinical status of the patient.

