16.3 Analysis Plan (to be evaluated in each arm independently)

16.31 Primary Outcome Analyses:

16.311 Definition: The primary endpoint of this trial is the proportion of patients who achieve a confirmed response to single-agent MK-3475. A confirmed response is defined to be a PR, nPR, CCR, CRi or CR (Arms A and B) or PMR, CMR, PR or CR (Arm C) noted as the objective status at any time while on single-agent MK-3475. All patients meeting the eligibility criteria who have signed a consent form and have begun treatment will be evaluable for response, with the exception of patients determined to be a major violation. For CLL patients with Richter's transformation, confirmed response is determined by response criteria defined for Richter's transformation.

16.312 Estimation: In each arm, the proportion of successes will be estimated by the number of successes divided by the total number of evaluable patients in that arm. Exact binomial confidence intervals for the true success proportion will be calculated. In addition, the confirmed response rate for all Richter's transformation patients (9 patients from Arm A and all patients in Arm C) will be calculated.

16.32 Secondary Outcome Analyses (to be evaluated in each arm independently; Arm C analyses may include the 9 Richter's transformation patients from Arm A): (For all outcomes associated with combination therapy in Arms A and C, disease measurements obtained after the last cycle of single-agent therapy are set as the baseline measurements for combination therapy).

16.321 Progression-free survival (PFS) for single-agent MK-3475 is defined as

the time from registration to the earliest date of documentation of disease progression while on single-agent MK-3475 or death due to any cause. In Arm A and Arm C, patients who initiate combination therapy for stable disease after 3 months of single-agent MK-3475 will be censored on the date that combination therapy is initiated.

In Arm A and Arm C, PFS for the combination of MK-3475 and the signal inhibitor is defined as the time from initiation of treatment with the combination therapy to the earliest date of documentation of disease progression while on combination therapy or death due to any cause.

The distribution of progression-free survival will be estimated using the method of Kaplan-Meier.

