16.322 Treatment-free survival (TFS) for single-agent MK-3475 is defined as the time from registration to the date of initiation of subsequent treatment for CLL/SLL or lymphoma or death due to any cause. In Arm A and Arm C, the initiation of combination therapy with MK-3475 and the signal inhibitor will be considered subsequent treatment.

In Arm A and Arm C, TFS for the combination of MK-3475 and the signal inhibitor is defined as the time from initiation of combination therapy to the date of initiation of subsequent treatment for CLL/SLL or death due to any cause.

The distribution of treatment-free survival will be estimated using the method of Kaplan-Meier.

16.323 The time to next treatment (TNT) for single-agent MK-3475 is defined as the time from registration to the date of initiation of subsequent treatment for CLL/SLL or lymphoma. In Arm A and Arm C, the initiation of combination therapy with MK-3475 and the signal inhibitor will be considered subsequent treatment.

In Arm A and Arm C, TNT for the combination of MK-3475 and the signal inhibitor is defined as the time from initiation of combination therapy to the date of initiation of subsequent treatment for CLL/SLL.

The distribution of time to next treatment will be estimated using the method of Kaplan-Meier.

16.324 The complete response rate will be estimated by the number of patients who achieve a CRI or CR (Arms A and B) or CMR or CR (Arm C) divided by the total number of evaluable patients. Complete response rate will be evaluated for single-agent MK-3475 in each arm and also for the combination of MK-3475 and the signal inhibitor in Arm A and C. All evaluable patients will be used for this analysis. Exact binomial 95% confidence intervals for the true complete response rate will be calculated in each arm.

16.325 Duration of response (DR) is defined for all evaluable patients who have achieved a PR, nPR, CCR, CRI, or CR (Arms A and B) or PMR, CMR, PR or CR (Arm C) as the date at which the patient's objective status is first noted to be a PR, nPR, CCR, CRI, or CR (Arms A and B) or PMR, CMR, PR or CR (Arm C) to the earliest date relapse is documented. Duration of response will be evaluated for single-agent MK-3475 in each

arm and also for the combination of MK-3475 and the signal inhibitor in Arm A and C. The distribution of duration of response will be estimated using the method of Kaplan-Meier.

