16.326 Overall survival is defined as the time from registration to death due to any cause. The distribution of overall survival will be estimated using the method of Kaplan-Meier.

16.327 Arm A and Arm C: The overall response rate for the combination of MK-3475 and the signal inhibitor (targeted agents) will be estimated by the number of patients with an objective status of CR, CRi, nPR, CCR or PR (Arm A) or PMR, CMR, PR or CR (Arm C) while on the combination therapy divided by the total number of evaluable patients. All evaluable patients who receive the combination therapy will be used for this analysis. Exact binomial 95% confidence intervals for the true overall response rate to the combination will be calculated. In addition, the responders on this study will be further examined in an exploratory manner to determine if there are any patterns in prognostic factors or disease characteristics, including whether the patient had a Richter's transformation or Ibrutinib-resistant disease, for both single-agent MK-3475 and combination therapy responders.

16.328 Adverse Events: All eligible patients that have initiated treatment will be considered evaluable for assessing adverse event rate(s). The maximum grade for each type of adverse event will be recorded for each patient, and frequency tables will be reviewed to determine patterns. Additionally, the relationship of the adverse event(s) to the study treatment will be taken into consideration. Adverse events will be evaluated for single-agent MK-3475 in each arm and also for the combination of MK-3475 and the signal inhibitor in Arm A and Arm C.

16.33 Correlative Analyses:

16.331 PD-1, PD-L1 and PD-L2 will be measured for each patient at baseline and during treatment. Each measure will be summarized descriptively by median, min, max and interquartile range. Overall response and complete response will be correlated with each measure using Wilcoxon rank sum test. The relationship between each measure and time to event measures (DR, TNT, PFS) will be evaluated using Cox proportional hazard models.

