16.332 Markers of immune modulation and immune profiles will be summarized descriptively by median, min, max, and interquartile range (continuous factors) or frequency distribution (categorical factors) at each time point. Patterns over time will be summarized by absolute difference or relative change. Changes across time will be assessed using paired analyses, including Wilcoxon signed rank tests for continuous measures and McNemar's tests for categorical measures. Overall response and complete response will be correlated with continuous factors using Wilcoxon rank sum tests. Jitplots will be used to visually examine differences between groups for continuous factors. Overall response and complete response will be correlated with categorical factors using Fisher's exact tests.

16.34 Over Accrual: If more than the target number of patients are accrued, the additional patients will not be used to evaluate the stopping rule or used in any decision making processes; however, they will be included in final endpoint estimates and confidence intervals.

16.4 Safety Analysis Phase (Arm A and B only):

A safety analysis will be performed after the first 12 patients (6 each arm for Arm A and B) have been accrued to the study. Accrual will be temporarily halted while these patients are followed for one cycle to assess adverse events. If 2 or more of the first 6 patients in either arm experience a DLT as defined below, then accrual will continue to be temporarily suspended to the arm affected. All toxicity data will be reviewed by the study team and a decision will be made about whether the starting dose needs to be adjusted or the protocol should be continued.

Toxicity will be measured per NCI-CTCAE version 4. DLT is defined as an adverse event possibly, probably, or definitely related to study treatment that meets one of the following:

- hepatic toxicity defined as AST or ALT  $> 5 - 10 \times$  ULN for  $> 4$  weeks; Total bilirubin  $> 5 \times$  ULN for  $> 4$  weeks ; Concurrent AST or ALT  $> 3 \times$  ULN and total bilirubin  $> 2 \times$  ULN (excluding liver involvement by CLL or lymphoma) for  $> 4$  weeks (potential Hy's Law case)
- grade 4 non-hematological toxicity[except weight loss or fatigue or laboratory abnormalities not associated with clinical sequelae] lasting longer than 4 weeks despite of holding therapy and supportive treatments
- Any grade 5 AE

16.5 Data & Safety Monitoring:

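### The combination complete response rate in section 16.324 is divided by all evaluable patients, including those who never receive the combination, unlike the paired response rate in section 16.327

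*Combined protocol and SAP*

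**What the plan says.** Secondary goal 2.26 sets the two combination rates side by side: "Test the overall and complete response rates of MK-3475 in combination with the signal inhibitor". The analysis plan then treats them in two places.

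- **Section 16.324 (CR rate).** The number of complete responders is divided by the total number of evaluable patients. The scope covers both regimens: "Complete response rate will be evaluated for single-agent MK-3475 in each arm and also for the combination of MK-3475 and the signal inhibitor", the latter in Arms A and C. The analysis set follows: "All evaluable patients will be used for this analysis".
- **Section 16.327 (combination overall response rate, ORR).** The opening sentence also divides by the total number of evaluable patients, but counts only responses recorded on the combination. The next sentence narrows the set: "All evaluable patients who receive the combination therapy will be used for this analysis".

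Section 16.311 defines the term. Eligible patients who gave consent and "have begun treatment will be evaluable for response, with the exception of patients determined to be a major violation". Nothing in that definition refers to the combination.

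Section 7.3 says who can receive it. In Arms A and C, after progression at any time on single-agent MK-3475, or stable disease at the month-3 evaluation, "a commercially available FDA-approved CLL signal inhibitor can be added to MK-3475".

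**The concern.** Recipients of the combination are a selected subset of Arms A and C. A patient whose single-agent response lasts never becomes a candidate, and a candidate need not be given the inhibitor. If 16.324 is followed as written, each of these patients enters the combination denominator and cannot enter the numerator.

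Two consequences follow. First, the reported combination CR rate depends on how many patients went on to the combination as well as on what it achieved. The more durable the single-agent responses, the lower the combination figure. Second, the CR rate and ORR for one regimen, joined in one objective, would have different denominators. Even if every combination response were complete, the CR rate would fall below the ORR whenever some evaluable patients did not receive the combination. Section 16.6 commits the trial to reporting its secondary endpoints publicly, so the two figures could appear together.

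**Working it through.** **Plan's own figures.** The documents give no figure for the combination CR rate or for the size of its analysis set, so there is nothing to reproduce on the disputed point. The surrounding design figures do reproduce by exact binomial calculation. At least 5 responses in 23 gives 0.073 at a true rate of 10% and 0.864 at 30% (stated: 0.07 and 0.86). At least 5 in 17 gives 0.099 at 15% and 0.874 at 40% (stated: 0.10 and 0.87). The point here does not touch them.

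**Inputs.** N is the number of evaluable patients: 23 for Arm A and 17 for Arm C (section 16.12). Let m be the number of evaluable patients who receive the combination, and x the number of complete responses on it. Neither m nor x is in the documents, so all values below are assumptions. Intervals are exact 95%, the type named in 16.324.

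**Formula.** The rate among recipients is x/m. The rate under a literal 16.324 is x/N = (x/m) × (m/N). The relative understatement is 1 − m/N.

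**Main example, Arm C, x = 3, m = 10.**
- Among recipients: 3/10 = 30% (7-65%).
- Under 16.324: 3/17 = 18% (4-43%).
- Check: 0.30 × 10/17 = 0.176.

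**Range, x = 2.**

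| Arm | Under 16.324 | Recipients only, by assumed m |
|---|---|---|
| A | 2/23 = 8.7% (1.1-28.0) | m=20: 10.0% (1.2-31.7); m=16: 12.5% (1.6-38.3); m=12: 16.7% (2.1-48.4); m=8: 25.0% (3.2-65.1) |
| C | 2/17 = 11.8% (1.5-36.4) | m=15: 13.3% (1.7-40.5); m=12: 16.7% (2.1-48.4); m=9: 22.2% (2.8-60.0); m=6: 33.3% (4.3-77.7) |

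The relative understatement runs from 1 − 20/23 = 13% to 1 − 8/23 = 65% in Arm A, and from 1 − 15/17 = 12% to 1 − 6/17 = 65% in Arm C.

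**Numerator.** Section 16.327 ties responses to time on the combination. Section 16.324 has no such condition, so it does not say in which phase a complete response must be noted to count for the combination.

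**The case against.** The best counter-argument is that the author meant evaluable to be read by treatment phase. It has support. Section 16.327 itself uses the total number of evaluable patients for a rate that it then restricts to recipients, so the phrase need not mean everyone who began treatment. Section 16.328 handles adverse events in similar shorthand for both regimens, and it would be odd to put never-exposed patients in a combination adverse-event denominator. Sections 11.0 and 16.32 reset the baseline to the end of single-agent therapy, and a patient who never starts the combination has no assessment against that baseline.

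This makes a per-phase intention plausible, but it does not settle the text. The note in 16.32 resets measurements and does not redefine the population. In 16.327 a further sentence was needed to narrow the set; in the corresponding position, 16.324 names all evaluable patients. No other section supplies the restriction. The objection does establish that 16.327 is not a clean model: its opening sentence carries the same loose denominator and needs the same repair. If that sentence governed, the two denominators would match, but both rates would then be diluted.

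It is also fair that the illustrative intervals overlap widely. They come from the same three events, however. The issue is which quantity is being estimated, and overlap does not resolve that.

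**Conclusion.** The point holds as an error of specification in one secondary, descriptive endpoint in Arms A and C. Read literally, 16.324 multiplies the combination CR rate by recipients/evaluable and breaks its comparability with the combination ORR, taking the recipient restriction in 16.327 as governing. It should be corrected. No test or decision rule uses the rate.

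The size is unknown. The fall from 30% to 18% rests on an assumed 3 CRs and 10 recipients, with 17 evaluable patients.

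Three stronger readings are tempting but not supported:

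- A reader might infer a larger dilution because "Arm C analyses may include the 9 Richter's transformation patients from Arm A", and because of over-accrued patients "they will be included in final endpoint estimates and confidence intervals". Adding nine patients while holding recipients at 10 assumes that none of the nine received the combination, which the documents do not say. The three reserve places in Arm C exist to cover ineligibility, cancellation and similar losses, so 17 is the natural denominator for illustration.
- A reader might infer that the combination definitions of treatment-free survival and time to next treatment miss therapy for transformed disease, because they omit lymphoma. The single-agent wording also has to cover Arm B, and the protocol calls Arms A and C the CLL arms. This is a difference of wording, not a shown loss of events.
- A reader might infer that overall survival from registration (16.326) is wrong for the combination. It is a correct definition for each arm.

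**What to change.** In 16.324, separate the two regimens. Keep all evaluable patients as the denominator for the single-agent CR rate. For the combination, count CR or CRi (Arm A) and CMR or CR (Arm C) noted during combination therapy, and divide by the evaluable patients who receive it.

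In 16.327, add the restriction to recipients to the denominator in the opening sentence, so that it agrees with the sentence after it.

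The cost is about one sentence in 16.324 and a short qualifier in 16.327. No new data appear to be needed, because recipients must already be identified for the combination ORR. Making the change before the analysis also removes a choice of denominator that could otherwise be made after results are seen. Reporting both counts, evaluable patients and recipients, would let a reader check either rate.

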- An unacceptable adverse event that occurs after the patient received at least 2 cycles of treatment, which in the opinion of the Investigator, precludes further trial participation.

13.5 Event Monitoring: Patients will enter event monitoring for the following reasons:

- If the patient develops evidence of PMD/PD (For CLL Arm A and C: PMD/PD on combination therapy; For B-NHL Arm B: PD on MK-3475 single therapy) during treatment or OBSERVATION by examination, blood counts, or imaging as defined in Sections 11.23, 11.4, 11.54 and 11.61, they will be considered to have progressed and will enter EVENT MONITORING. Refer to Section 4.0 for required tests at PMD/PD.

NOTE: Patients whose only evidence of disease recurrence is by sensitive evaluation of MRD will continue under OBSERVATION in accord with standard clinical practice and will NOT be considered PD.

- Subsequent treatment for CLL or NHL
- Failure to return for an evaluation during OBSERVATION
- Patient refusal of further study treatment or noncompliance
- Patient develops an intercurrent illness that precludes further participation, or requires a prohibited concomitant treatment
- The Investigator withdraws the patient in the patient's best interests
- Administrative reasons (e.g., the patient is transferred to hospice care)
- Pregnancy
- An unacceptable adverse event that occurs during cycles 1-2

**Note:** When a subject discontinues treatment, all applicable activities scheduled for the final trial visit should be performed at the time of discontinuation. Any adverse events which are present at the time of discontinuation/withdrawal should be followed in accordance with the safety requirements outlined in Section 10.0 -Assessing and Recording Adverse Events

13.6 A patient is deemed ineligible if after registration, it is determined that at the time of registration, the patient did not satisfy each and every eligibility criteria for study entry. The patient will go directly to the event-monitoring phase of the study:

- If the patient received treatment, all data up until the point of confirmation of ineligibility must be submitted. Event monitoring will be required per Section 18.0 of the protocol.
- If the patient never received treatment, on-study material and the End of Active Treatment/Cancel Notification Form must be submitted. No further data submission is necessary.

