- 13.7 A patient is deemed a major violation, if protocol requirements regarding treatment in cycle 1 of the initial therapy are severely violated that evaluability for primary end point is questionable. All data up until the point of confirmation of a major violation must be submitted. The patient will go directly to the event-monitoring phase of the study.
- 13.8 A patient is deemed a cancel if he/she is removed from the study for any reason before any study treatment is given. On-study material and the End of Active Treatment/Cancel Notification Form must be submitted. No further data submission is necessary.

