## 16.0 Statistical Considerations and Methodology

16.1 Overview: This Phase II study will utilize a one-stage binomial design in each arm independently (Arms A, B, and C) to assess the overall response rate associated with single-agent MK-3475 in patients with relapsed and progressive CLL/SLL, including CLL patients with Richter's transformation (RS) or Hodgkin's transformation (Arm A and Arm C) and other types of relapsed and progressive low grade B cell NHL including FL, WM and marginal zone lymphoma (Arm B).

16.11 Endpoint: The primary endpoint of this trial is the proportion of patients who achieve a confirmed response to single-agent MK-3475. A confirmed response is defined to be a PR, nPR, CCR, CRi or CR (Arms A and B) or CMR, PMR, PR, or CR (Arm C) noted as the objective status at any time while on single-agent MK-3475. All patients meeting the eligibility criteria who have signed a consent form and have begun treatment will be evaluable for response, with the exception of patients determined to be a major violation.

16.12 Sample Size: This study is expected to require a maximum of 23 evaluable patients each in Arm A and Arm B. We anticipate accruing 1 additional patient in each arm to account for ineligibility, cancellation, major treatment violation, or other reasons. Therefore, this study is expected to accrue between 46 - 48 patients in these two arms.  
As of MCCC Addendum 3, due to promising response observed in CLL patients with Richter's transformation, an additional arm (Arm C) with 17 evaluable patients is added to the trial. We anticipate accruing 3 additional patients to account for ineligibility, cancellation, major treatment violation, or other reasons for a total of 20 patients on Arm C. These patients will be accrued to allow better evaluation of response and toxicity of single agent MK 3475 in patients with Richter's transformation. This study is now expected to accrue a maximum of 68 patients.

16.13 Accrual Rate and Study Duration: The anticipated accrual rate is approximately 2-4 patients per month. Therefore, the accrual period for this phase II study is expected to be approximately 2-3.0 years. The final analysis can begin as soon as the last patient has been observed for 6 months, or at approximately 3.0-3.5 years.  

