16.51 The principle investigator(s) and the study statistician will review the study at least twice a year to identify accrual, adverse event, and any endpoint problems that might be developing. The Mayo Clinic Cancer Center (MCCC) Data Safety Monitoring Board (DSMB) is responsible for reviewing accrual and safety data for this trial at least twice a year, based on reports provided by the MCCC Statistical Office.

16.52 Adverse Event Stopping Rules (to be evaluated in each arm independently for single-agent MK-3475 and separately for combination therapy): The stopping rules specified below are based on the knowledge available at study development. We note that the Adverse Event Stopping Rule may be adjusted in the event of either (1) the study re-opening to accrual or (2) at any time during the conduct of the trial and in consideration of newly acquired information regarding the adverse event profile of the treatment(s) under investigation. The study team may choose to suspend accrual because of unexpected adverse event profiles that have not crossed the specified rule below.

Single-agent MK-3475: Accrual will be temporarily suspended to the affected arm if at any time we observe events considered at least possibly related to study treatment during cycles with single-agent MK-3475 (i.e. an adverse event with attribute specified as "possible," "probable," or "definite") that satisfy one of the following:

- If 4 out of the first 12 treated patients experience a DLT as defined in Section 16.4

- If after the first 12 patients have been treated, 30% of all patients experience a DLT as defined in Section 16.4.

Combination of MK-3475 and signal inhibitor (Ibrutinib or Idelalisib) in Arm A and Arm C: Initiation of treatment with the combination (addition of Ibrutinib or Idelalisib) will be halted in Arm A and Arm C if at any time we observe events considered at least possibly related to study treatment during cycles with the combination (i.e. an adverse event with attribute specified as “possible,” “probable,” or “definite”) that satisfy one of the following:

- If 2 out of the first 6 treated patients experience a DLT as defined in Section 16.4
- If after the first 6 patients have been treated, 30% of all patients experience a DLT as defined in Section 16.4.

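### Adverse event rates omit treated patients later found ineligible, and the AST/ALT dose-limiting toxicity criterion literally excludes isolated values above 10 × ULN

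*Combined protocol and SAP*

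**What the plan says.** **Adverse event set.** Section 16.328 states: "All eligible patients that have initiated treatment will be considered evaluable for assessing adverse event rate(s". Section 13.6 treats a patient as ineligible if it emerges after registration that, at registration, "the patient did not satisfy each and every eligibility criteria for study entry". It then covers those who were already dosed: "If the patient received treatment, all data up until the point of confirmation of ineligibility must be submitted". Such patients go straight to event monitoring. Never-treated patients are a separate class under 13.8: "A patient is deemed a cancel if he/she is removed from the study for any reason before any study treatment is given". For Arm C, section 16.12 says: "We anticipate accruing 3 additional patients to account for ineligibility, cancellation, major treatment violation, or other reasons". That gives 20 accrued for 17 evaluable. Arms A and B each allow one extra patient beyond 23.

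**Stopping rules.** The rules in 16.52 are "to be evaluated in each arm independently for single-agent MK-3475 and separately for combination therapy". They count treated patients, or all patients, without an eligibility condition. One single-agent rule reads: "If after the first 12 patients have been treated, 30% of all patients experience a DLT as defined in Section 16.4". The first combination rule reads: "If 2 out of the first 6 treated patients experience a DLT as defined in Section 16.4".

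**DLT definition.** Section 16.4 requires an event at least possibly related to treatment that meets one of these limbs:

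- AST or ALT at > 5 - 10 × ULN for more than 4 weeks
- total bilirubin above 5 × ULN for more than 4 weeks
- AST or ALT above 3 × ULN together with bilirubin above 2 × ULN for more than 4 weeks
- a grade 4 non-hematologic toxicity lasting more than 4 weeks, with an exception for laboratory findings that have no clinical consequences
- any grade 5 event

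**The concern.** An eligibility filter can be defended for a response endpoint. For harm it has no clear rationale, because harm follows exposure. Safety is a secondary goal in every arm (2.21, 2.24). As written, the population in the final safety tables can differ from the one monitored under 16.52, and in arms this small one patient can remove a rare event from a table.

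The DLT point concerns the formal count that suspends accrual or halts combination starts. If the AST/ALT limb has an upper end, the count is not monotone in severity: a worse liver signal can score lower than a milder one. All four rules in 16.52 use this definition. It matters most for the combination, since section 15.27 describes AST/ALT elevations above 5 × ULN with idelalisib.

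**Working it through.** **Plan figures.** The documents state no operating characteristics for the 16.52 rules, so there is no safety figure to reproduce. The efficacy tables do reproduce: P(X ≥ 5 | n = 23) is 0.073 at a true rate of 0.10 and 0.864 at 0.30, against the stated 0.07 and 0.86; P(X ≥ 5 | n = 17) is 0.099 at 0.15 and 0.874 at 0.40, against 0.10 and 0.87. Neither point touches them.

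**Part 1: can a treated patient be found ineligible?** Yes. Besides 13.6 itself, 6.5 requires treatment to start within 14 days of registration, while 17.2 allows central pathology review, where needed, up to 42 days after registration. No other section returns these patients to the adverse event rates.

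Let N be the number treated, m the number of those found ineligible, x the patients with the event and y those among the m. The all-treated rate is x/N; the 16.328 rate is (x − y)/(N − m). Take N = 20, Arm C's planned accrual, and x = 1. The documents do not give m, so a range is shown. If the event falls at random, y = 1 with probability m/N.

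| m | All treated | 16.328 rate if event is in an ineligible patient | Probability | 16.328 rate otherwise |
|---|---|---|---|---|
| 0 | 1/20 = 5.0% | not applicable | 0 | 1/20 = 5.0% |
| 1 | 1/20 = 5.0% | 0/19 = 0% | 1/20 = 5% | 1/19 = 5.3% |
| 3 | 1/20 = 5.0% | 0/17 = 0% | 3/20 = 15% | 1/17 = 5.9% |

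The row m = 3 is an extreme: it uses the whole Arm C allowance, which also covers cancels, who are never treated. Under random placement the average is unchanged (for m = 1, 0.95 × 1/19 = 1/20). Systematic bias therefore needs a link between failing an entry criterion and risk of harm.

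**Part 2: does an isolated rise above 10 × ULN meet any limb?** Assume a related, non-fatal AST/ALT elevation held at the stated level for more than 4 weeks, with bilirubin not above 2 × ULN and no clinical sequelae.

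| Level held | AST/ALT limb | Bilirubin limb | Concurrent limb | Grade 4 limb | DLT |
|---|---|---|---|---|---|
| 8 × ULN | met | not met | not met | not met or excepted | yes |
| 12 × ULN | not met (above band) | not met | not met | not met or excepted | no |

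A patient who passes 10 × ULN but also spends more than 4 weeks between 5 and 10 × ULN would still count.

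Apply this to two patients among the first six on combination, where 2 DLTs halt combination starts:

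| Levels held | DLTs as written | DLTs with open > 5 × ULN |
|---|---|---|
| 8 and 8 | 2/6, halt | 2/6, halt |
| 8 and 12 | 1/6, no halt | 2/6, halt |
| 12 and 12 | 0/6, no halt | 2/6, halt |

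No event rate is assumed there. For scale only, assume a true DLT rate of 0.30 and let a share s of DLTs be uncounted rises above 10 × ULN. The probability of reaching a rule is P(X ≥ k | n, 0.30 × (1 − s)):

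| s | 4 of 12 | 2 of 6 |
|---|---|---|
| 0 | 0.51 | 0.58 |
| 0.10 | 0.41 | 0.51 |
| 0.25 | 0.28 | 0.41 |
| 0.50 | 0.09 | 0.22 |

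Both the 0.30 and the shares are assumptions; the documents give no frequency of values above 10 × ULN.

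**The case against.** **Part 1 may have no consequence.** There may be no treated ineligible patients. The allowances are 1, 1 and 3 for all reasons combined. No direction of bias is shown. Grade 3 and 4 events are collected regardless of attribution (10.61), and expedited reporting is unaffected. All of this stands and limits the weight. It gives no reason for the filter.

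**The denominator of 20 could be larger.** Section 16.32 lets Arm C analyses include the 9 Richter's patients from Arm A, giving 29. One ineligible patient then moves 1/29 (3.4%) to 0/28 or 1/28 (3.6%), a smaller shift. That is fair, but the pooling is optional, and 20 is Arm C's own planned accrual.

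**Including these patients mixes truncated with full follow-up.** Data are required only up to confirmation of ineligibility, so their late events may be missed and rates diluted. This is a real cost, and the fix should flag it.

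**The DLT wording is a drafting slip that nobody would apply literally.** Probably so: note 2 under 8.3 uses an open threshold above 5 × ULN for autoimmune hepatitis. But a formal count should not rest on readers correcting the text.

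**Other safeguards cover the gap.** Section 8.3 withholds MK-3475 for non-hematologic toxicity of grade 3 or worse and stops therapy for autoimmune hepatitis above 5 × ULN. Chemistry is checked before each cycle, section 15.27 describes idelalisib elevations as reversible on interruption, and the DSMB reviews safety at least twice a year. Section 16.52 lets the team suspend accrual or adjust the rule at its discretion. These make prolonged values above 10 × ULN less likely and reduce the harm. They act on individuals or by judgement and do not repair the count. The discretionary sentence also speaks of accrual, whereas the combination rule halts combination starts in patients already enrolled.

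**Conclusion.** Both points hold on the text. Section 16.328 drops treated patients later found ineligible from the adverse event rates of every arm. The size is unknown and may be nil; for one such patient among 20 and a single event, the 5.0% rate becomes 0% or 5.3%. The AST/ALT limb in 16.4 is wrong as written: under the literal reading, and for isolated elevations without sequelae, two combination patients at 12 × ULN count as 0/6 where two at 8 × ULN count as 2/6.

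Expected practical impact is small. Arm A closed to accrual in April 2016 and Arm B in April 2017, so for accrual and combination starts the DLT wording now matters mainly in Arm C. The safety-set wording affects the final tables of all three arms. The corrections should be made because they cost almost nothing, not because harm has been shown.

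**What to change.** - **16.328:** define the adverse event set as all patients who received at least one dose of study treatment, regardless of eligibility. Footnote any patient whose data stop at confirmation of ineligibility.
- **16.4:** write the AST/ALT limb as > 5 × ULN for > 4 weeks, with no upper end.

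Neither edit needs new visits, tests or patients. The first brings in a few patients with possibly truncated follow-up, which the footnote discloses. The second could trigger a suspension or halt slightly earlier, which is what the rule is for.
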